A 24-Week, Randomized, Double-blind, Placebo-controlled Clinical Study to Evaluate the Efficacy and Safety of Proso Millet and Wheat Extract(Keranat™) on Hair Health

Brief Title	Evaluate the Efficacy and Safety of Proso Millet and Wheat Extract(Keranat™) on Hair Health							
Protocol Number	NC07-NOVA-2022							
Study Design	Randomized, Double blind, Parallel Assignment							
Name of product(s)	Keranat™(proso millet and wheat extract) 300 mg/capsule, and respective matched Placebos.							
Indication	Hair health / Dietary supplement							
Phase	Interventional- Dietary supplement							
Enrollment:	100 (50 Experimental, 50 Placebo Comparator)							
How to eat	Take 1 capsules 2 times daily for 24 weeks							
Sponsor/CRO	Novarex / Nutracore							
Site	Korean Skin Research Center(KSRC) [name]							

### 1. Background

Millet (Panicum miliaceum) and its main compound, miliacin, arouse a lot of interest in dermatological research, especially for its tissue repair and wound healing properties. Miliacin, also called Panicol or Prosol, belongs to the class of organic compounds known as triterpenoids. Miliacin is a white odorless solid crystal practically fat- and water-insoluble. Cellular studies using thymocyte and splenocyte cultures have revealed a protective effect of miliacin from DNA fragmentation and apoptosis. Animal and clinical studies with suppurating wounds in different physiopathological conditions have confirmed and deepened these first results. Thanks to its strong anti-inflammatory properties, topical application of millet oil promoted rapid cleansing of the wounds and significantly activated the reparative processes. More recent studies focusing on miliacin have showed that it improved cellular renewal and proliferation and promoted the process of hair growth. When normal human keratinocytes derived from the foreskin were exposed to miliacin (6 mg/mL), the metabolic capacity of these cells was increased (+162%) and their proliferation was also stimulated (215%). Miliacin, the main triterpenoid from millet, is known to stimulate keratinocyte metabolism and proliferation. Polar lipids are able to form vesicles with active compounds and to improve their bioavailability.

# 2. Trial objective and endpoint

# 2.1. Objectives

The purpose of this randomized, double-blind, placebo-controlled study will be to evaluate whether the daily intake of Keranat™ for 24 weeks can promote the gloss and elasticity of hairs, improve their density and strength, and reduce hair loss.

#### 2.1.1. Primary Objective

- To evaluate the change in hair elasticity between the Keranat™ and placebo group at baseline and 24 weeks, as measured by Expert 7601Tension Testing System.
- To evaluate the change in hair gloss between the Keranat™ and placebo group at baseline and 24 weeks, as measured by Skin-Glossy meter GL200.

### 2.1.2. Secondary Objective

- To evaluate the change in hair thickness improvement between the Keranat™ and placebo group at baseline and 24 weeks, as measured by microscope and ToupLite software.
- To evaluate the change in the ratio of anagen hair between the Keranat™ and placebo group at baseline and 24 weeks, as measured by Image-Pro® 10 program.
- To evaluate the change in the number of hair loss between the Keranat™ and placebo group at baseline and 24 weeks. Collected and counted the number of lost hair.
- To evaluate the change in the number of hairs per unit area between the Keranat™
  and placebo group at baseline and 24 weeks, as measured by Folliscope PS.
- To evaluate the change in hair distribution score through clinical photography between the Keranat™ and placebo group before and after intake. This evaluates improvement and deterioration on a 7-point scale, with higher scores meaning improvement. By comparing photos before and after intake, if there is no change, 0 points, improvement is a maximum of 3 points, and worsening is a minimum of -3 points.
- To evaluate the change in Hair health improvement between the Keranat™ and placebo group at baseline and 24 weeks. The evaluation was conducted through Patient Report Outcome(PRO) using a standardized survey form. Survey allowing for participant-report changes in hair health because of intervention using a 7-point scale.
- To evaluate the change in serum levels of cytokines through clinical photography between the Keranat™ and placebo group at baseline and 24 weeks.

#### 2.2. Trial Endpoints

### 2.2.1. Primary Endpoints

- The change of hair elasticity: Change of the week 24 from baseline
- The change of hair gloss: Change of the week 24 from baseline

### 2.2.2. Secondary Endpoints

- The change of hair thickness: Change of the week 24 from baseline
- The change of anagen hair ratio(%): Change of the week 24 from baseline
- The change in hair loss amount: Change of the week 24 from baseline
- The change of number of hair per unit area: Change of the week 24 from baseline
- The change of hair distribution score through clinical photography: Change of the week 24 from baseline
- Self-reported Hair health assessments: Change of the week 24 from baseline
- The change of serum levels of cytokines (IL-1, TNF-α, PGE2): Change of the week
   24 from baseline

### 2.3.3. Safety Endpoints

 Incidence and severity of adverse events (clinical, laboratory measurements, hormone measurement, hCG)

Safety will be assessed through routine monitoring of adverse events, evaluation of hematological and blood chemistry values, regular measurement of vital signs, and physical examination at selected trial visits (according to the trial schedule).

#### 3. Selection of Patients

#### 3.1. Inclusion Criteria

- Age 19 and 60
- Hair gloss score of 3 or less and a hair damage score of less than 18 according to the visual evaluation classification method.
- Willing to maintain the same hairstyle, hair color, hair length, and hair regimen throughout the study period.
- Subject must be able to comprehend and voluntarily sign study procedures and consent forms.

#### 3.2. Exclusion Criteria

- Those diagnosed with and receiving treatment for the alopecia within 3 months before screening (androgenetic alopecia, alopecia areata, Telogen effluvium, etc.)
- Use of that may affect hair or hair loss symptoms treatment medicine, dietary

supplements, or treatments containing herbal medicine ingredients within 3 months before screening.

- Any active scalp or skin disease that may interfere with the study treatment and evaluations.
- Pregnancy or breastfeeding or planning pregnancy.
- Case of abnormal values at creatinine (excess at the upper limit of the reference range)
- Case of abnormal values at ALT or AST (2 times excess at the upper limit of the reference range)

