# 5. Study setting and design

This randomized controlled study will be conducted at the Korean skin research center(KSRC) in South Korea.

This will be a 24-week, randomized, double-blind, parallel group, placebo-controlled trial with two arms, as summarized below:

- Arm 1 (Placebo arm): placebo; 300 mg capsule twice a day
- Arm 2 (Test group 1): Keranat™; proso millet and wheat extract; 150 mg/capsule twice a day

Study subjects who voluntarily consent to the study at visit 1 (week 0) will be judged for eligibility according to inclusion and exclusion criteria. Selected subjects will be randomly assigned to study groups and tested for functional biomarkers after ingesting the experimental or control foods for 24 weeks.

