#### 7. Treatments

### 7.1. Investigational Products

Investigational products supplied for this will include:

Keranat™ 300mg capsules or matching placebos in PTP packaging are going to be supplied to Subjects.

Keranat™ capsules are containing 150mg of proso millet and wheat extract.

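### Nothing in the eligibility criteria excludes a volunteer with known allergy to the ingredients, or diagnosed coeliac disease, from a wheat and millet extract taken for 24 weeks

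*Combined protocol and SAP*

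**What the plan says.** The summary table at the front of the protocol names the product as "Keranat™(proso millet and wheat extract) 300 mg/capsule, and respective matched Placebos" and gives the regimen as "Take 1 capsules 2 times daily for 24 weeks". Section 7.1 repeats the composition: "capsules are containing 150mg of proso millet and wheat extract". The front table and section 7.1 describe the amount per capsule differently. That needs reconciling, but this point does not depend on it.

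Section 5 says that consenting volunteers "will be judged for eligibility according to inclusion and exclusion criteria", and section 4 assigns random numbers on the same basis.

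Section 3.1 has four inclusion criteria: age, hair gloss and damage scores, an unchanged hair regimen, and capacity to consent. Section 3.2 has six exclusions. The first begins "Those diagnosed with and receiving treatment for the alopecia within 3 months before screening". The others cover medicines, supplements or herbal treatments that may affect hair; "Any active scalp or skin disease that may interfere with the study treatment and evaluations"; "Pregnancy or breastfeeding or planning pregnancy"; raised creatinine; and raised ALT or AST.

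Section 6 schedules a history at screening. It does not say what the history must ask, and no criterion acts on an allergy found there.

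**The concern.** The list already screens for safety through pregnancy, kidney function and liver enzymes. It omits the one hazard that can be read directly from the product's name. Wheat is a food allergen, and the participants are volunteers taking a dietary supplement for hair appearance, so there is little benefit to set against an avoidable reaction.

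The schedule adds some weight. After the baseline visit, the next visit and the first scheduled adverse-reaction check are at week 8 (±7). Until then the written safeguard is what happens at screening, and on this point the screening criteria are silent.

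At stake is the safety of a small number of individuals, possibly none. The primary comparison is not at stake.

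**Working it through.** **Step 1. Does any criterion cover the case?** Take a volunteer with known wheat allergy or diagnosed coeliac disease and no active skin signs, and apply each criterion in turn.

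| Criterion | Excludes this volunteer? |
|---|---|
| Inclusion: age | No |
| Inclusion: gloss and damage scores | No |
| Inclusion: constant hair regimen | No |
| Inclusion: understanding and consent | No |
| Exclusion: treated alopecia | No |
| Exclusion: hair-affecting medicines, supplements or herbal treatments | No |
| Exclusion: active scalp or skin disease | Only if the condition shows as active skin disease that may interfere |
| Exclusion: pregnancy, breastfeeding or planned pregnancy | No |
| Exclusion: creatinine | No |
| Exclusion: ALT or AST | No |

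None of the ten criteria covers the case directly. One might catch it incidentally. There is no investigator-discretion exclusion, and the list shows no redaction or gap where such a line could have stood. No other section mentions allergy, intolerance, gluten or coeliac disease.

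**Step 2. How likely is it that such a person is enrolled?** The plan gives no figure to reproduce and no prevalence. The only input from the documents is 50 subjects on active product (front table and section 8.1). Let q be the proportion of volunteers with wheat allergy or coeliac disease. The values of q below are assumptions, shown as a range.

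P(at least one carrier among 50) = 1 − (1 − q)^50, and the expected number of carriers = 50 × q.

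| Assumed q | P(at least one) | Expected number |
|---|---|---|
| 0.2% | 1 − 0.998^50 = 0.095 | 0.10 |
| 0.5% | 1 − 0.995^50 = 0.222 | 0.25 |
| 1.0% | 1 − 0.990^50 = 0.395 | 0.50 |

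**Step 3. What these figures do and do not measure.** They give the chance that a carrier is present, not the chance of a reaction. They include undiagnosed carriers, whom a history question would not find. They take volunteers to be as likely to carry either condition as the assumed population, although people who know they have a wheat allergy are less likely to volunteer for a wheat capsule. For a given q, they are therefore an upper bound on what the added exclusion could prevent in the active arm.

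**Step 4. Effect on the efficacy comparison.** Even at q = 1%, the expected number is half a subject among 50. Section 8.1 allows for 20% dropout, which is 0.20 × 50 = 10 subjects per group. One extra withdrawal is small beside that.

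**The case against.** The strongest reply is that the hazard is presumed. The documents do not say how the extract is made or whether it retains wheat protein or gluten. Section 1 describes the activity in terms of miliacin, a triterpenoid, and polar lipids. If no protein remains, the risk may be very small, and for coeliac disease the matter turns entirely on gluten content. This stands as a limit on the size of the risk. It does not remove the omission, because nothing in the documents rules the risk out.

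A second reply is that ordinary care would catch the case. Wheat is in the product's name, a history is taken at screening, and consent material, which is not part of the copy reviewed, may carry a warning. This also stands in part: it lowers the chance that such a person enrols. But it relies on individual caution where a written criterion would settle the matter.

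A reader might also infer three stronger things, which the documents do not support:

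- **That a site is obliged to enrol such a volunteer.** The text makes the volunteer eligible. It nowhere compels a site to enrol everyone who qualifies.
- **That reactions are predictable.** This needs composition data that the documents do not give.
- **That reactions would fall in the active arm only, causing treatment-related dropout and unblinding.** This assumes a wheat-free placebo, and the placebo ingredients are not stated. Even if it were so, Step 4 shows that the effect on the comparison would be negligible.

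**Conclusion.** The omission is real and can be verified from sections 3.1, 3.2 and 5 alone. Applied as written, the criteria leave a volunteer with known wheat allergy or diagnosed coeliac disease eligible for a product described as a wheat and millet extract.

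Confidence in the omission is high. Confidence in the size of its consequence is low, because the extract's wheat protein or gluten content and the placebo ingredients are unknown. The range of about 10% to 39% for at least one carrier among 50 on active product is illustrative. It rests on assumed prevalences of 0.2% to 1%, and should be read as an upper bound on carriers, not as a reaction rate.

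This is a subject-safety point that is worth correcting because the correction is so cheap. It gives no reason to doubt the efficacy comparison.

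**What to change.** Add one exclusion to section 3.2: *known allergy or hypersensitivity to wheat, millet or any other ingredient of the test or placebo capsule; or diagnosed coeliac disease, unless the sponsor has documented that the product is gluten-free.* Ask about it in the history already scheduled at screening in section 6.

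In section 7.1, state the ingredients of both capsules and whether the extract contains wheat protein or gluten. If the sponsor holds evidence that none remains, it should cite that evidence and justify any narrower wording.

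The cost is one criterion, one history question and possibly a very small number of volunteers excluded. No laboratory test, extra visit or change of sample size is needed.

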#### 4. Randomization

A random number will be assigned during visit 1 (week 0) in the order in which the subject is enrolled according to the inclusion and exclusion criteria. Subjects will be assigned to the study group, based on a random list prepared by a third party independent of the study before the study begins. Study participants will be allocated to the control group, and the test group (KeranatTM) at a 1:1 ratio using a block randomization method. The study will be double-blind and group assignments will not be disclosed to investigators or subjects until the end of the study.

# 5. Study setting and design

This randomized controlled study will be conducted at the Korean skin research center(KSRC) in South Korea.

This will be a 24-week, randomized, double-blind, parallel group, placebo-controlled trial with two arms, as summarized below:

- Arm 1 (Placebo arm): placebo; 300 mg capsule twice a day
- Arm 2 (Test group 1): Keranat™; proso millet and wheat extract; 150 mg/capsule twice a day

Study subjects who voluntarily consent to the study at visit 1 (week 0) will be judged for eligibility according to inclusion and exclusion criteria. Selected subjects will be randomly assigned to study groups and tested for functional biomarkers after ingesting the experimental or control foods for 24 weeks.

#### 6. Schedule of Events

ltem	Screening -21~-D1	Pre-V1 D-3	V1 D0	V2 8w±7	V3 16w±7	V4 24w-3	V5 24w±7
history	•		•	•	•	•	•
Physical measurement	•	Х	X	•	•	X	•
Drinking and smoking history	•	X	X	•	•	X	•
Hair damage assessment	•	X	X	X	X	X	Х
Clinical photography (DSLR)	X	Х	•	•	•	X	•
Hair elasticity	Х	X	•	X	X	X	•
Hair gloss	•	Χ	•	•	•	X	•
Hair thickness	Х	X	•	X	X	X	•
Hair loss amount	Х	Χ	•	Χ	X	X	•
Self-reported Hair health assessments	Х	X	•	X	Х	X	•
anagen hair ratio(%)	Χ	Χ	•	X	Χ	Χ	•
IL-1, TNF-α, PGE2	Χ	Χ	•	Χ	Χ	Χ	•
Laboratory measurements	•	•	Χ	X	X	X	•
Adverse reaction	Х	Χ	Χ	•	•	•	•
Vital sigh	•	Х	•	•	•	Х	•
Dietary intake	Х	Х	•	Х	Х	Х	•
Physical activity	Х	Χ	•	X	Χ	Χ	•
Life habits	Х	Х	•	Х	Х	X	•
Compliance check	Х	Χ	Χ	•	•	Χ	•

#### 7. Treatments

### 7.1. Investigational Products

Investigational products supplied for this will include:

Keranat™ 300mg capsules or matching placebos in PTP packaging are going to be supplied to Subjects.

Keranat™ capsules are containing 150mg of proso millet and wheat extract.

# 7.2. Dosage

All treatment arms consider the regimens in fixed doses. Keranat™ 300mg and placebo are administered in two separate daily doses for 24 weeks.

### 8. Statistical Analysis Plan

The Statistical Analysis Plan will be written after the protocol finalization and definitely finalized before breaking the blind mode, prior to the first database lock. These specifications will detail the implementation of all statistical analyzes planned according to the main features reported in the protocol.

#### 8.1. Sample size determination

This study hypothesizes that the use of Keranat™ will improve hair health. Therefore, a primary comparison will be conducted between the placebo arm and the test arm(Keranat™).

To calculate the number of test subjects, based on a 24-week intake study similar to this clinical trial, the change in hair count per unit area (Mean  $\pm$  SD) of the test group was assumed to be 16.9  $\pm$  15.6 and the control group was 4.5  $\pm$  14.9. (d=12.4)

- (1)  $H_0: \mu t = \mu c \text{ VS } H_1: \mu t \neq \mu c$
- (2) At the 5% significance level, the type 2 error is 0.2, maintaining 95% power. ( $\alpha$  = 0.05,  $\beta$  = 0.2, statistical power =95%)
- (3) test group : placebo group = 1:1(k=1)
- (4) Calculation program: G\*power 3.1.9.2

As a result of calculating the number of subjects using G\*power 3.1.9.2, the number of subjects was calculated to be 41 per group and a total of 82. After considering the dropout rate of 20%, the number of subjects was calculated to be 50 per group and a total of 100.

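### The sample size is justified on a secondary endpoint, so power for the two primary endpoints is not established, and the stated type 2 error contradicts the stated power

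*Combined protocol and SAP*

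**What the plan says.** Section 2.2.1 of the combined protocol and SAP names two primary endpoints: "The change of hair elasticity: Change of the week 24 from baseline" and "The change of hair gloss: Change of the week 24 from baseline". Section 2.1.1 gives each its own instrument: elasticity "as measured by Expert 7601Tension Testing System" and gloss "as measured by Skin-Glossy meter GL200". Number of hairs per unit area appears in section 2.2.2, among the secondary endpoints.

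Section 8.1 introduces the calculation as serving a primary comparison of Keranat with placebo. Its inputs, however, are "based on a 24-week intake study similar to this clinical trial, the change in hair count per unit area": 16.9 ± 15.6 in the test group and 4.5 ± 14.9 in the control group, a difference of 12.4. The error rates are given as "the type 2 error is 0.2, maintaining 95% power", and the same pair is repeated in symbols. The result is that "the number of subjects was calculated to be 41 per group and a total of 82". On attrition: "After considering the dropout rate of 20%, the number of subjects was calculated to be 50 per group".

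Section 8.2 sets a two-sided 0.05 threshold and does not say how the two primary endpoints combine into a trial conclusion.

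**The concern.** A sample-size section should show that the planned number is adequate for the endpoints on which the trial will be judged. Here the only power figure concerns a different outcome, measured on a different scale with a different device. No expected effect or SD is given for elasticity or gloss, and no reason is offered why hair count can stand in for them. Because section 8.1 speaks of a primary comparison, a reader may well take 95% as the power of the primary analysis. If elasticity or gloss then gave a null result, there would be no planned sensitivity to read it against.

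The power statement is also inconsistent in itself. A type 2 error of 0.2 means 80% power, and 95% power means a type 2 error of 0.05.

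Finally, power for two primary endpoints is not defined until the plan says whether both or at least one must be significant.

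**Working it through.** **Inputs.** From section 8.1: mean changes 16.9 and 4.5, SDs 15.6 and 14.9, 1:1 allocation, alpha 0.05, 20% dropout, 50 enrolled per group. From section 8.2: two-sided testing and an independent t-test among the listed methods. Power is computed from the exact noncentral t distribution with 2n − 2 degrees of freedom and noncentrality δ·√(n/2), where n is the number per group and δ the standardised effect.

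**Step 1: reproduce the plan's figure (hair count).**
- Pooled SD = √((15.6² + 14.9²)/2) = √((243.36 + 222.01)/2) = 15.254.
- δ = 12.4 / 15.254 = 0.813.

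| n per group | Power for hair count |
|---|---|
| 24 | 78.7% |
| 25 | 80.4% |
| 40 | 94.8% |
| 41 | 95.3% |

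The smallest n is 41 for 95% power and 25 for 80%. The stated 41 is therefore correct for hair count at 95% power, and 0.2 is the entry that does not fit. One-sided testing does not give 41 either: on the pooled SD it needs 20, 27 and 34 per group for 80%, 90% and 95% power.

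**Step 2: after dropout.** 50 × (1 − 0.20) = 40 per group, one fewer than the calculated 41. Power for hair count is 94.8%, so the shortfall is negligible.

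**Step 3: primary endpoints.** The documents supply no δ for elasticity or gloss, so their power cannot be computed. For illustration only, with assumed effects at 40 per group and two-sided alpha 0.05 for each endpoint:

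| Assumed δ | Power per endpoint |
|---|---|
| 1.0 | 99% |
| 0.8 | 94% |
| 0.6 | 75% |
| 0.4 | 42% |

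Solving the other way, 40 per group detects δ = 0.63 with 80% power and δ = 0.82 with 95% power.

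**Step 4: two primaries together.** Power here means the chance of overall success, assuming equal effects on both endpoints and 40 per group.
- *Both must succeed at 0.05 each.* Under independence each endpoint needs power √0.80 = 0.894 or √0.95 = 0.975.
- *At least one succeeds at 0.025 each (Bonferroni).* Under independence each endpoint needs power 1 − √0.20 = 0.553 or 1 − √0.05 = 0.776.

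The correlation of 0.5 is an assumption. Those figures come from 300,000 simulated trials per point; the same simulation at correlation 0 returned the exact values.

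| Success rule | Correlation | δ for 80% | δ for 95% |
|---|---|---|---|
| Both | 0 | 0.73 | 0.89 |
| Both | 0.5 | 0.71 | 0.88 |
| At least one | 0 | 0.54 | 0.68 |
| At least one | 0.5 | 0.59 | 0.76 |

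**The case against.** The best case for the plan has four parts.

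1. *Nothing shows that 50 per group is too few.* This is true. The trial may be well powered for elasticity and gloss, and the point is only that section 8.1 does not show it.
2. *The 0.2 is a labelling slip.* This is very probably right: 95% appears in both words and symbols, 41 follows from 95%, and 0.2 did not enter the calculation. It is the smaller part of the point. The line still carries two incompatible values and needs correcting.
3. *Section 8.1 ties its inputs openly to hair count and never says that 95% applies to the primaries.* This is also true as written. But the section presents the calculation as support for the primary comparison and offers no other, so the primaries are left without any justification.
4. *Section 8 leaves analysis details to a SAP finalised before unblinding.* A success rule could properly be set there, and the scenarios in Step 4 rest on assumptions that the sponsor has not made. The deferral covers how analyses are implemented; it does not supply the missing sample-size inputs.

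One caution stands. The figure of 40 treats the 20% dropout as the only loss. Section 8.2 bases efficacy on a per-protocol set that also excludes major deviations and entry-criteria failures, and section 8.1 does not say whether the 20% covers these. If only 35 per group were analysed (an illustration), hair-count power would be 91.8% and the effect detectable with 80% power would be 0.68.

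**Conclusion.** The concern holds. The number 41 per group is correctly calculated, but for a secondary endpoint. The documents establish no power for either primary endpoint, and the stated type 2 error is wrong beside the stated power. The two values correspond to 25 and 41 per group, and only 41 matches the plan.

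Whether the trial is adequate for elasticity and gloss is unknown. With 40 per group, the 95% figure would apply to one of them only if its true standardised effect were about 0.82 or more. This rests on the t-test, two-sided alpha 0.05 for each endpoint, and 20% as the total loss. The figures would differ for the analysis of covariance or the Wilcoxon test, which section 8.2 also lists.

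**What to change.** Revise section 8.1 as follows.

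1. Change the type 2 error to 0.05, in words and symbols. State that 41 per group and 95% power refer to the secondary endpoint hair count per unit area, and that with 50 enrolled and 20% dropout 40 remain, giving 94.8% power. Say whether the 20% includes exclusions from the per-protocol set.
2. Do not present 95% as the power for the primary endpoints. Give the expected difference, SD and source for elasticity and for gloss. If these are not available, state the standardised difference detectable at 40 per group for each endpoint: 0.63 (80% power) and 0.82 (95% power). This fallback is weaker, because without an SD it cannot be read in instrument units.
3. Add one sentence saying whether both primaries or at least one must succeed, and at what alpha, with the matching detectable difference from Step 4 and its assumptions. Only the row for the chosen rule is needed.

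The cost is a rewording of section 8.1, with no added patients, visits or measurements. The one disadvantage to the sponsor is that 95% can no longer be read as the power of the primary analysis.

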#### 8.2. Definition of trial populations included in the analysis

- The efficacy analyses will be performed on the PPS(Per protocol set), defined as all randomized subjects by their assigned treatment arms.
- The PPS(Per protocol set) will be defined as subjects receiving randomized treatment, who meets entry criteria, have not permanently discontinued treatment administration and had no major protocol deviation
- Additionally, efficacy analyses will be performed on a FAS(Full Analysis Set).
- All safety analyses will be performed on the Safety Set, defined as all patients who
  received at least one dose of the treatment.
- Tests of normality will be performed to evaluate the data distribution. Test group of continuous variables will be compared to the placebo group using Independent T-

test, analysis of covariance, and the Wilcoxon rank-sum test. Comparison between groups according to changes in time will be analyzed using Paired T-test. Categorical data will be analyzed using the chi-square test or Fisher's exact test. A two-sided test will be considered significant when the p value <0.05.

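### Section 8.1 pairs a type II error of 0.2 with 95% power, and its 50 per group less 20% dropout leaves 40, one short of the 41 required

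*Combined protocol and SAP*

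**What the plan says.** All the figures are in section 8.1 (Sample size determination) of the combined protocol and SAP.

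- **Assumed effect.** The calculation uses the change in hair count per unit area over 24 weeks: 16.9 (SD 15.6) on the test product and 4.5 (SD 14.9) on control, a difference of 12.4.
- **Error rates.** The text reads "At the 5% significance level, the type 2 error is 0.2, maintaining 95% power". The bracket that follows repeats the pair in symbols: β is 0.2 and "statistical power =95" per cent.
- **Allocation and test.** Allocation is 1:1 and the alternative hypothesis is that the means differ. Section 8.2 confirms the sidedness: "A two-sided test will be considered significant when the p value <0.05".
- **Required number.** From G\*Power, "the number of subjects was calculated to be 41 per group and a total of 82".
- **Enrolled number.** "After considering the dropout rate of 20%, the number of subjects was calculated to be 50 per group and a total of 100". No formula is given for this step, and the number expected to remain after dropout is not stated.

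**The concern.** Two figures in the sample-size justification do not agree with their neighbours.

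First, the type II error and the power are complements, and 0.2 and 95% do not add to one. The clash appears in words and again in symbols, so it is unlikely to be one mistyped character, and nothing elsewhere in the document settles it. A reader who takes the 0.2 at face value cannot reproduce the sample size, and cannot tell whether the trial was planned for 80% or 95% power.

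Second, the number enrolled should leave the required number once the assumed dropout has occurred, and 50 per group does not leave 41. Losses bear directly on the analysis here. Section 8.2 bases the efficacy analyses on a per-protocol set that excludes subjects who stop treatment permanently or have a major deviation.

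**Working it through.** **Inputs** (section 8.1 unless noted): mean changes 16.9 and 4.5; SDs 15.6 and 14.9; allocation 1:1; α = 0.05, two-sided (sections 8.1 and 8.2); stated β 0.2; stated power 95%; 41 per group required; 20% dropout; 50 per group enrolled.

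**Step 1: standardised effect.**

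- Pooled SD = √[(15.6² + 14.9²)/2] = √[(243.36 + 222.01)/2] = √232.685 = 15.254
- Standardised effect = 12.4/15.254 = 0.813

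**Step 2: reproduce the plan's 41.** For an independent two-sample t-test with n per group, power comes from the noncentral t distribution with 2n − 2 degrees of freedom and noncentrality 0.813 × √(n/2). The smallest n that reaches each target is:

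| Target power | Implied β | Two-sided n per group | Power at that n | One-sided n per group |
|---|---|---|---|---|
| 80% | 0.20 | 25 | 80.4% | 20 |
| 90% | 0.10 | 33 | 90.2% | 27 |
| 95% | 0.05 | **41** | 95.3% | 34 |

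Of these combinations, only the two-sided test at 95% power gives 41. The normal approximation gives 40 at 95% power and 24 at 80%, so the conclusion does not depend on the method.

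**Step 3: which of the two figures is wrong.** The 41 was obtained with 95% power, so β = 1 − 0.95 = 0.05. The printed 0.2 is four times that (0.2/0.05 = 4). A calculation that used β = 0.2 would have given 25 per group (50 in total). The plan's 41 is 64% more than that (41/25 = 1.64).

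**Step 4: dropout.**

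- Remaining after the stated dropout: 50 × (1 − 0.20) = 40, one below 41.
- Enrolment needed to leave 41: 41/(1 − 0.20) = 51.25, so 52 per group (104 in total). Inflating the total instead gives 82/0.8 = 102.5, so 103.
- A possible origin of the 50: 41 × 1.2 = 49.2, rounded up to 50. This multiplies by one plus the dropout rate instead of dividing by one minus it. The plan shows no formula, so this is an inference.
- Dropout that 50 per group can absorb: (50 − 41)/50 = 9/50 = 18%.

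**Step 5: effect on power** (same t-test and same hair-count assumption).

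| Evaluable per group | Power |
|---|---|
| 40 | 94.8% |
| 41 | 95.3% |
| 50 | 98.1% |

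**The case against.** The strongest reply is that neither error changes the trial. The 0.2 was evidently not used: the 95%, the 41 and the 82 agree with one another, and enrolment, significance level and analysis do not depend on the misprinted value. On this view it is a wrong label, and setting 41 against 25 compares the plan with a design nobody proposed. The dropout shortfall is one subject per group. It takes power about 0.2 percentage points below 95%, and the 20% is itself a planning guess. The document states no number retained after dropout, so the 40 is derived and contradicts no printed figure. Finally, the power figures concern hair count, a secondary endpoint in section 2.2.2, while the primary endpoints in section 2.2.1 are elasticity and gloss. Quoting 94.8% to a decimal could lend precision to a figure that does not describe the primary comparisons.

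Much of this stands. The dropout point is minor and should not be presented as a meaningful loss of power. The 64% shows which figure is wrong and does not measure harm. Any restated power must be tied to the hair-count assumption. What does not stand is the inference that no correction is needed. The type II error is a core design parameter, and the printed pair is mathematically impossible. The enrolment figure, under the usual meaning of a dropout rate, does not deliver the number the same paragraph says is required.

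**Conclusion.** The statement is wrong as written, in two respects of unequal weight.

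- **Type II error.** It should be 0.05, not 0.2. The plan's own 41 per group settles this, and the 41 itself is correct.
- **Dropout allowance.** Fifty per group covers 18% dropout, not 20%. At 20%, 40 per group remain and power is 94.8%, just under the 95% target. This slip does not leave the trial underpowered on its own assumption.

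The result rests on the means and SDs in section 8.1, a two-sided 5% independent t-test, and the reading of dropout as a proportion of those enrolled. It applies to change in hair count only and gives no information about power for elasticity or gloss.

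**What to change.** In section 8.1:

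1. Replace the type II error of 0.2 with 0.05, both in the sentence and in the bracket, and leave the power at 95%.
2. Keep 50 per group (100 in total) and correct the allowance in one of two ways. Either say that with 20% dropout 40 per group are expected to be evaluable, giving 94.8% power under the hair-count assumption, or say that 50 per group allows for 18% dropout from the required 41.

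If the sponsor prefers to keep both 20% dropout and 41 evaluable, enrolment would have to be 52 per group (104 in total). The gain of about half a percentage point in power (94.8% to 95.3%) hardly calls for it.

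The recommended correction is to text only. It needs no extra subjects and no change to procedures or analysis. Its only cost is that the stated power after dropout, or the stated dropout allowance, becomes slightly less favourable.
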